### Exclusion Criteria:

- Hematuria without appropriate workup
- Pelvic organ prolapse beyond the hymen
- Clinically relevant urinary retention
- Pelvic reconstructive surgery within 6 months
- Reconstructive pelvic surgery with "mesh kits"
- Clinically relevant nephrolithiasis
- History of breast cancer
- Contraindication to topical estrogen therapy
- Anticoagulation therapy
- Prior pelvic or vaginal radiation therapy
- Prior gynecologic malignancy
- Undiagnosed genital bleeding

# Subject Recruitment

Patients will be recruited from both the Departments of Gynecology and Urology. We estimate that the two departments evaluate >200 women with rUTI per year. We anticipate realistic recruitment of 1/3 of these patients that meet inclusion criteria. We will recruit 94 patients per power calculation described above and anticipate completion of recruitment in 2 years. For Specific Aim 2, we will perform microbiome analysis on 1/3 of these patients for a total of 32 patients. Further collection of samples will be frozen for future analysis once external funding is secured.

Patients may also be recruited from Social Media, either from a Mayo-approved Facebook ad or from Twitter.

# **Subject Randomization**

Patients will be randomized using 6 as a block size to make sure the balance of the randomization at any time point. The randomization will be created by **stored** and stored in REDcap. The coordinator who is going to do the randomization will get access to the REDcap randomization schedule and get the treatment assignment from there for the eligible patients.

# **Data Collection**

Demographic information will be collected, which will include age, race, and comorbidities. Urinary cultures will be collected from prior to studies and subsequent to enrollment, with details of results documented. MESA questionnaire will be used to assess baseline and subsequent urinary symptoms to evaluate for change following the procedure as a secondary outcome. DIVA questionnaire will assess change to sexual function and symptoms of GSM at baseline and following treatment. All the data will be collected and entered in the REDcap database.

# **Statistical Analysis**

The 4-month rUTI prevalence and 6-month rUTI prevalence will be estimated using binomial method and compared between the two groups using Chi-square test or Fisher's exact test when applicable. The 6 month rUTI recurrence rate will be estimated using Poisson method and compared between the two groups using GEE method.

Overdispersion will be evaluated and if presented, negative binomial method will be used to estimate the rUTI recurrence rate.

Time to first recurrent UTI will also be compared between the two groups using log-rank test.

The MESA responses, DIVA responses and vaginal histology changes over time will be summarized and compared between the two groups using general linear mixed model or generalized linear mixed model when appropriate.

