Fractional CO2 LASER vaginal therapy has recently been studied for the treatment of GSM. LASER therapy is currently commercially available and has FDA clearance for use in gynecology. Current evidence shows that with treatment, histologic changes of the vaginal epithelium have shown regeneration to a premenopausal state, along with subjective improvement in GSM symptoms and sexual function. Using LASER therapy, Zerbinati et al described response by the vaginal epithelium with thickening, superficial shedding and renewing of stratified epithelium, which was maintained 2 months after treatment.[4] Athanasiou et al also described the impact of LASER therapy on the vaginal flora, decreasing the vaginal pH to 4.7 (p<0.001) and increasing the Lactobacillus colonies from 30% to 79%.[5] Based on the impact this promising new regenerative therapy has on the vaginal epithelium and microbiome, we anticipate this may have a positive impact on women with rUTI.

- We therefore hypothesize that fractional CO2 LASER vaginal therapy is non-inferior to topical vaginal estrogen therapy for the treatment of rUTI.
  a. Primary Outcome: Improvement in recurrence of culture positive UTI
- 2. We also hypothesize that LASER therapy will improve the urinary and vaginal microbiome, decreasing the uropathogenic presence and increasing Lactobacillus.
  - a. Measurement 1: The number of UTI with UPEC isolated from patients
  - b. Measurement 2: The pH of the vagina as a proxy for presence of Lactobacillus sp.
  - c. Measurement 3: Categorize vaginal and urinary microbial communities

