# Methods

We propose a randomized controlled trial to evaluate the clinical difference between the LASER and topical vaginal estrogen in treating patients with rUTI. We expect to enroll 94 patients, to power this study to 80% with type I error of 5%, expecting a recurrence in UTI of 16% and non-inferior margin of 20%. This is accounting for a 10% drop out rate. While this clinical margin is wide, this project will provide us with ample data to apply for external funding, along with a wealth of microbiome data to evaluate in Aim 2. Menopausal women with rUTI will be recruited from the Departments of Urology and Gynecology. If they meet inclusion criteria, they will be randomized to treatment of topical vaginal estrogen or LASER therapy. LASER therapy will be applied 6 weeks apart for a total of 3 treatments. Topical vaginal estrogen will be prescribed per the patient's formulary and preference. Patients will be monitored for recurrence of culture positive UTI.

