# Vaginal Estrogen Protocol

Women randomized to vaginal estrogen therapy will be offered vaginal cream. Two FDA approved formulations exist and patients will be offered the choice between the two, which may also be dependent on their insurance formulary preference.

- 1. Conjugated estrogen (Premarin): 0.5 gm per vagina twice weekly
- 2. Estradiol (Estrace): 1gm per vaginal twice weekly

**Specific Aim 1:** Evaluate the number of culture positive, symptomatic UTI in women following randomization to vaginal estrogen and vaginal LASER therapy.

Methods: Following randomization and treatment initiation, patients will be monitored for recurrence of UTI. Patients will be encouraged to call the treating physician for treatment antibiotics according clinical judgment. Standard urine cultures will be obtained along with information about what type of antibiotic treatment was administered. Validated questionnaires will also be collected to monitor symptoms of GSM and also of urinary incontinence symptoms (Appendix A and B). Patients will be followed for 6 months with evaluations at baseline, 4 months, and 6 months.

**Specific Aim 2:** Characterize the urinary and vaginal microbiome at baseline and at 4 months of patients in each group.

Methods: Baseline vaginal and catheterized urine samples will be collected along with samples at 4 months. Standard catheterized urine cultures will be performed and if symptomatic, treated appropriately (per Aim 1). Microbiome of urine and vaginal environments will then be analyzed using 16S ribosomal DNA sequencing along with shotgun metagenomics. For this study, we will perform sequencing and metagenomics on the first 16 patients in each arm (32 patients total). The remaining collection will be biobanked for future analysis. These techniques will allow us to measure the abundance of different bacteria, but also evaluate the genetic variation and evolutionary effect from treatment. This will also allow us to evaluate for the differences in the microbiome between responders and non-responders in each treatment arm, considering factors such as UTI, symptoms, pH, etc.

Vaginal Estrogen arm	Baseline	4 months	6 months (if can be completed within the funding period)
Informed consent	X		
Vaginal pH	X	X	Х
Vaginal swab collection	X	X	X (banked)
Urine collection	Х	Х	X (banked)
MESA questionnaire	X	Х	Х
DIVA questionnaire	Х	Х	X

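### The trial is hypothesised and sized for non-inferiority on a 20% margin, but the planned analysis of UTI recurrence never uses the margin

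*Combined protocol and SAP*

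**What the plan says.** - **Hypothesis.** The Background states that "fractional CO2 LASER vaginal therapy is non-inferior to topical vaginal estrogen therapy for the treatment of rUTI". The Recurrent UTI section repeats non-inferiority as the goal.
- **Primary outcome.** "Primary Outcome: Improvement in recurrence of culture positive UTI", with no time point.
- **Sample size.** Methods gives 94 patients, 80% power, 5% type I error and 10% dropout, "expecting a recurrence in UTI of 16% and non-inferior margin of 20" per cent. It does not state whether the 5% is one- or two-sided, or whether the margin is absolute. The margin appears nowhere else.
- **Analysis.** Statistical Analysis estimates 4-month and 6-month prevalence by a binomial method, "compared between the two groups using Chi-square test or Fisher's exact test when applicable". It compares the 6-month rate by Poisson/GEE (negative binomial if overdispersed) and time to first recurrence by log-rank.
- **Follow-up.** Specific Aim 1 says "Patients will be followed for 6 months with evaluations at baseline, 4 months, and 6 months". Both visit tables head the last column "6 months (if can be completed within the funding period" and have no row for UTI.

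**The concern.** The chi-square, Fisher and log-rank tests take no difference as their null hypothesis, and the GEE comparison has no other null specified. A non-inferiority claim needs the opposite: rejection of the hypothesis that LASER is worse by the margin or more. A non-significant result from the planned tests cannot do this, because it covers results that meet the margin and results that do not. A significant result in LASER's favour would support the claim, but the sample size reproduces only with equal rates, so that is not the scenario the trial was planned on.

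Two outcomes are then possible. Either the primary question goes unanswered, or the interval method, its level and the time point are chosen once the data are known.

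**Working it through.** **Inputs.** From Methods: 16% recurrence, 20% margin, 5% type I error, 80% power, 10% dropout, 94 enrolled. Assumed: 16% in both arms (only one rate is given), an absolute margin, one-sided 5%, and 1:1 allocation. The last is implied by patients being "randomized using 6 as a block size to make sure the balance of the randomization at any time point" but is not stated as a ratio.

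**Step 1: the plan's own figure.**

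n per arm = (z₀.₉₅ + z₀.₈₀)² × 2p(1−p) / margin²
= (1.645 + 0.842)² × 2 × 0.16 × 0.84 / 0.20² = 41.5, so 42.

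Total 84; 84 / 0.9 = 93.3, so 94. This reproduces. One-sided 2.5% gives 53 per arm and 118 enrolled. A superiority test of 16% v 36% gives 59 to 85 per arm. So 94 is a non-inferiority size for a difference in proportions, and the matching analysis is a two-sided 90% interval.

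**Step 2: what non-significance covers.** Take 42 per arm and 7/42 recurrences on estrogen. The 90% upper limits are by Miettinen-Nurminen (MN) and the chi-square is uncorrected, two-sided 5%.

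| LASER | Difference (points) | Upper 90% limit (points) | Chi-square p | Margin met? |
|---|---|---|---|---|
| 7/42 | 0.0 | 13.9 | 1.00 | yes |
| 9/42 | 4.8 | 19.2 | 0.58 | yes |
| 10/42 | 7.1 | 21.8 | 0.42 | no |
| 14/42 | 16.7 | 31.8 | 0.078 | no |

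Chi-square is non-significant for LASER counts of 2 to 14, and Fisher for 1 to 15. The margin is met only up to 9, and Wald, Newcombe and MN agree on that cut-off.

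**Step 3: how often this matters.** Exact binomial enumeration at 42 per arm:

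- True rates 16% and 16%: chi-square is non-significant in 94.7% of trials. Of all trials, 75.4% are non-significant and meet the margin (MN 90%), and 19.3% are non-significant and do not.
- True rates 36% (LASER) and 16%: chi-square is non-significant in 43.4%. The 90% margin rule wrongly declares non-inferiority in 4.9%.

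**Step 4: the interval has to be named in advance.** Power with 16% in both arms:

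| Rule | n per arm | MN | Wald |
|---|---|---|---|
| 90% interval | 42 | 78.0% | 80.0% |
| 90% interval | 44 | 80.8% | not needed |
| 95% interval | 42 | 69.0% | 71.7% |
| 95% interval | 53 | 77.9% | 80.3% |
| 95% interval | 56 | 80.2% | not needed |

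With 10% dropout, rounded up to equal arms: 88 / 0.9 = 97.8, so 98; 106 / 0.9 = 117.8, so 118; 112 / 0.9 = 124.4, so 126.

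Type I error of the 90% rule, for estrogen rates from 2% to 30%, is 4.4–5.6% with MN and 4.9–7.4% with Wald. Wald's excess lies at low rates: 6.7% at an estrogen rate of 5% and 7.3% at 2%. At 16% both are about 4.9%.

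**The case against.** The plan nowhere says that a non-significant test will be read as non-inferiority. Its binomial estimates and the GEE model could supply an interval that an analyst compares with 20 points. On this view the defect is an unstated rule rather than a wrong one, and the 43.4% arises only if non-significance is misread. That condition is fair and is kept in the verdict. It does not remove the gap: no interval for the difference is planned, and its level alone moves power from 78–80% to 69–72%. Nor can the rate or log-rank analyses stand in, because the only margin given fits a difference in proportions.

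Three narrower points also stand:

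- The 19.3% arises where LASER really is non-inferior, so it mainly reflects limited power. It shows that the p-value does not sort the results, not that the plan makes an error that often.
- At 14/42 the observed difference is below 20 points. Non-inferiority is not shown there, but neither is inferiority by the margin.
- Specific Aim 1 counts symptomatic culture-positive UTIs, the primary outcome omits symptoms, and Statistical Analysis speaks of rUTI prevalence. A first-event proportion fits the single 16%, but the sponsor must confirm the event.

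Methods concedes that the margin is wide and that the data are meant to support a funding application. Strategic Initiatives nevertheless promises level 1 evidence, so this does not excuse the omission.

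**Conclusion.** The concern holds and must be fixed. The primary hypothesis has a margin and a sample size that reproduces exactly, but no planned analysis tests it and no primary time point is named. With 7/42 on estrogen, LASER counts of 10 to 14 would give a non-significant chi-square without meeting the margin. If non-significance were taken as non-inferiority, the false-claim risk at a true 20-point deficit would be 43.4% instead of 4.9%. These figures assume 42 evaluable per arm, 1:1 allocation, an absolute margin, and 16% as the estrogen rate. The omission itself depends on none of them.

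**What to change.** **Statistical Analysis.** Make the primary analysis the LASER-minus-estrogen difference in the proportion of patients with at least one culture-positive UTI by one named time point. Declare LASER non-inferior if the upper limit of a pre-named two-sided 90% interval is below 20 percentage points. Reconcile the event definition with the symptomatic requirement in Specific Aim 1. Keep the chi-square/Fisher, rate and log-rank comparisons as supportive, and state that non-significance in them is not evidence of non-inferiority.

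**Methods.** State that the margin is absolute, that the 5% is one-sided, and that the 16% applies to both arms at the named time point.

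**Time point.** If 6 months is chosen, reconcile the unconditional follow-up in Specific Aim 1 with the funding-dependent visit column, and confirm that UTI capture to 6 months is unconditional. If 4 months is chosen, note that "LASER therapy will be applied 6 weeks apart for a total of 3 treatments" and that the LASER table puts the third at 3 months. Most of the counting window would then fall within the treatment course (the gap from baseline to first treatment is not given), and the 16% would need confirming for it.

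**Cost.** A few sentences. Any pre-named margin-based interval resolves the defect.

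- Wald 90%: no change to size or power.
- MN 90%, suggested for its steadier type I error: restate power as 78% at 94, or enrol 98 (4 more).
- Two-sided 95%, if preferred: restate power as about 69% (MN) to 72% (Wald) at 94, or enrol 118 with Wald or 126 with MN (24 or 32 more).

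### No UTI comparison pre-specifies adjustment for the pre-enrolment UTI count: a valid plan that passes up a small, nearly free gain in precision

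*Combined protocol and SAP*

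**What the plan says.** The Statistical Analysis section plans three kinds of UTI comparison. The 4- and 6-month prevalences are compared by chi-square or Fisher's exact test. For the rate, "The 6 month rUTI recurrence rate will be estimated using Poisson method and compared between the two groups using GEE method", with a negative binomial model if there is overdispersion. Time to first UTI is compared by log-rank test. No covariate is named for any of them.

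Under Subject Randomization, "Patients will be randomized using 6 as a block size to make sure the balance of the randomization at any time point"; no stratification factor is named.

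The baseline history is available. The Inclusion Criteria admit women on 3 positive cultures in 12 months or 2 in 6 months, and under Data Collection, "Urinary cultures will be collected from prior to studies and subsequent to enrollment, with details of results documented". No look-back window is given there.

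The size of the trial comes from the Methods section: "We expect to enroll 94 patients", "to power this study to 80% with type I error of 5" per cent, "expecting a recurrence in UTI of 16% and non-inferior margin of 20" per cent. It adds: "This is accounting for a 10% drop out rate".

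**The concern.** A woman's earlier UTI frequency is a natural predictor of her later UTIs. The entry rule sets a floor on the count but no ceiling, so women with very different histories may enrol. In a trial of this size the arms can differ by chance on that history. With 42 per arm, the difference in arm means of any baseline variable has a standard error of √(2/42) = 0.22 SD. A gap of more than 0.3 SD in either direction therefore has a probability of about 17%.

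Neither the randomisation nor the analysis accounts for such a gap. What is at stake is the width of the interval that has to clear the 20-point margin, and how convincing the result is if the arms do differ. If no covariate is named in advance, any later adjustment would also look data-driven.

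**Working it through.** **1. The plan's own figure.** Inputs from Methods: 16% recurrence (taken as equal in both arms), margin 0.20, 80% power, 5% type I error, 10% dropout. Allocation of 1:1 is assumed.

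- n per arm = (z₁₋α + z₁₋β)² × 2p(1−p) / margin² = (1.645 + 0.842)² × 2 × 0.16 × 0.84 / 0.04 ≈ 41.6, so 42.
- 42 / 0.9 = 46.7, so 47 per arm and **94 in total**, as stated.
- At one-sided 2.5% the formula gives 53 per arm and 118 in total, which does not match. The plan therefore implies one-sided 5%.

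The sample size thus rests on an unadjusted proportion, not on the rate model.

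**2. What a given gain is worth on that scale.** With 42 per arm, SE = √(2 × 0.16 × 0.84 / 42) = 0.080. Power is Φ(0.20/0.080 − 1.645) = 80.4%, and the 90% interval half-width is 1.645 × 0.080 = 13.2 points. If the covariate explains a share R² of the outcome variance, SE is multiplied by √(1 − R²):

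| R² | Power at 42 per arm | 90% half-width (points) |
|---|---|---|
| 0 | 80.4% | 13.2 |
| 0.02 | 81.1% | 13.0 |
| 0.05 | 82.1% | 12.8 |
| 0.10 | 83.9% | 12.5 |

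**3. How large R² might be.** The documents do not say, so it must be assumed. Each woman is given a stable UTI rate from a gamma distribution, with mean 1 or 3 per year before the entry filter and relative variance (frailty variance) 0.5, 1 or 2. Entry follows either route of the Inclusion Criteria. The covariate is log(12-month count). Recurrence is set to 16%, or to 36% (planned value plus margin), in both arms. About 1,500 trials of 42 per arm were simulated per setting. The table gives the variance of the adjusted estimate divided by that of the unadjusted one. Adjustment was by a Poisson model for the rate ratio and a linear model for the risk difference.

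| Mean rate, frailty variance | Log RR, 16% | Risk diff., 16% | Log RR, 36% | Risk diff., 36% |
|---|---|---|---|---|
| 1, 0.5 | 1.005 | 0.993 | 0.987 | 0.994 |
| 1, 1 | 0.993 | 0.991 | 0.970 | 0.977 |
| 1, 2 | 0.996 | 0.994 | 0.948 | 0.959 |
| 3, 0.5 | 0.988 | 0.978 | 0.948 | 0.959 |
| 3, 1 | 1.001 | 0.985 | 0.886 | 0.931 |
| 3, 2 | 0.954 | 0.946 | 0.866 | 0.913 |

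A separate simulation with the same entry rule gave 0.94–1.02 and 0.95–1.02 at 16%, and 0.84–1.00 and 0.92–0.99 at 36%. Ratios at or slightly above 1 mean no gain. Taking both sets together, the variance reduction is:

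- at 16%: about 0–6% on either scale;
- at 36%: about 0–16% for the log rate ratio and 1–9% for the risk difference (8.7% is the single highest cell; the separate simulation reached 8%).

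**4. Why the gain is small at 16%.** Without frailty, 16% recurrence corresponds to −ln(0.84) = 0.17 UTIs per woman in six months. At so low a rate most of the variation is Poisson noise that no covariate can explain. The entry rule also cuts off the lower end of the prior count, which weakens it as a predictor.

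**The case against.** The strongest reply is that nothing needs correcting. Randomisation makes the unadjusted comparison valid, and its standard error already allows for chance imbalance. At the planned recurrence the gain may be nil. This stands, and it limits the point to efficiency.

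Several stronger readings are tempting, but the documents do not support them:

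- *That precision is lost on a large scale.* Frailty simulations with 0.5 to 1.0 UTIs per woman in follow-up can show variance reductions of 11–23%. The plan implies about 0.17. The treated rate in the placebo-controlled estrogen trial cited in the Background, 0.5 per patient-year, is 0.25 per six months. The larger gains need rates about 2 to 6 times higher, together with frailty variance of 1 to 2.
- *That the rate model excludes covariates.* The sentence on GEE is silent. Only the chi-square, Fisher and log-rank tests are unadjusted as written.
- *That a covariate in the rate model helps the non-inferiority test.* The 20-point margin is on a proportion, so that comparison needs its own adjusted estimate.
- *That prior UTI frequency varies widely.* This is plausible, but the entry rule gives minimum counts only and no distribution.

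The covariate is also not quite ready-made. A woman who qualifies on 2 cultures in 6 months needs no 12-month record to enter, and women recruited through social media may have records elsewhere. This stands as a small cost. It does not block the change, because every eligible woman has at least 2 positive cultures in the past 12 months, so the logarithm is always defined.

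**Conclusion.** The omission is real and its consequence is modest. No UTI comparison specifies adjustment for the prior UTI count, although the trial uses that history for entry and records it. The plan as written is valid: no bias, type I error problem or sample-size error follows.

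On the scale of the margin, the gain at 16% recurrence is worth about two points of power at most (82.1% against 80.4% at R² = 0.05). It is larger if recurrence exceeds the plan, which is when precision is most needed. These figures assume gamma frailty with variance 0.5 to 2, individual risk that is stable before and after treatment starts, and 42 evaluable women per arm. None of these, except the 42 derived from the stated sample size, comes from the documents. The change is optional, and confidence is moderate.

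**What to change.** In the Statistical Analysis section:

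1. Define the baseline count as the number of culture-positive UTIs in the 12 months before enrolment. Use the culture thresholds of the Inclusion Criteria and the same window for both entry routes, and state how an incomplete history is handled.
2. Pre-specify the log of that count as a covariate in the Poisson or negative binomial GEE model.
3. For the 6-month proportion, report a standardised (g-computation) risk difference with its confidence interval, from a model with arm and that single covariate, beside the unadjusted difference. Name the variance method, and say in advance which of the two estimates decides non-inferiority. Methods ties the 20-point margin to a recurrence proportion without giving a time point. Six months, the end of follow-up ("Patients will be followed for 6 months with evaluations at baseline, 4 months, and 6 months"), is assumed here and should be confirmed.

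The sample size stays at 94. The cost is a few sentences, plus abstraction of a 12-month culture history for women who enter on 2 in 6 months. With about 0.16 × 84 ≈ 13 women expected to have a recurrence, the model should carry no further covariates.
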